Patients will be selected prospectively and randomly assigned to either the control group (standard exposure technique) or the suction-integrated Cobb group. Randomization will be performed with a coin toss: “best two out of three” style. For example, if “heads” represents the “control” group, 2 out of 3 tosses resulting in “heads” will assign a given patient to the control group, and if “tails” represents the “suction-integrated Cobb group” 2 out of 3 tosses resulting in “tails” will assign the patient to the suction-integrated Cobb group. Randomization will stop once 20 subjects are enrolled in the suction-integrated Cobb group. If at that time, the control group has less than 20 subjects, all subsequent subjects will be assigned to the control group.

During the consent process, patients will be informed that a new instrument may be used during their surgery. The risks of using the device will be explained to the patient, which will include the surgeon’s discomfort when using the new instrument, or failure of the device, which may lead to a delay during the exposure phase of surgery, which could ultimately result in a longer surgery. Surgeons will be given time to become familiar with the instrument. Operative data will be collected.

In the control group, the surgeons will utilize standard exposure technique and instruments. In the suction-integrated Cobb group, surgeons will be provided with the device. Standard equipment will also be readily available in case the surgeon decides for any reason not to use the device. The device will be provided by Ludwig Medical Corporation, the manufacturers of the device.

The following data will be recorded: age, gender, BMI, spinal levels involved, overall operative time, exposure time measured from skin incision until adequate exposure is achieved by the surgeon, blood loss during the exposure, and number of times the suction had to be unclogged.

No postoperative follow up is required.

A total of 40 patients will be randomized, with twenty assigned to each group.

6) Data Management*

All study staff will be CITI certified and will be trained in handling confidential medical information. Data will be stored on a password-protected computer in a secured location. Data will be coded and each subject will be assigned a unique study number. The linking code will be stored separately and will only be accessible to the study team. Only research members approved by the IRB will have access to the data.

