Power analyses has determined that 36 subjects (2 groups of 18) would be sufficient to demonstrate a significant effect. The parameters and assumptions of this analysis are as follows: an average exposure time with typical instruments of 30 (± 15) minutes, a 45% reduction in exposure time previously demonstrated in a previous small study with the new device, a 1:1 enrollment ratio for sub-groups, an alpha value of 0.05 for significance, and power value of 80%. Our proposed study size of 40 subjects will therefore confer statistical power.

7) Provisions to Monitor the Data to Ensure the Safety of Subjects

The PI will be responsible for data and safety monitoring. Any suspected or observed breach in data security will be reported to the PI and IRB.

The data collected and planned analyses are described above. Data will be collected before, during, and after each patient's surgery, and will be reviewed by study staff. The trial will be suspended if a breach of security is observed, or harm is demonstrated to subjects.

8) Withdrawal of Subjects

Subjects will be withdrawn from the study if their planned surgical procedure is cancelled or changed in such a way as to no longer meet inclusion criteria for the study. If a subject withdraws from the study, or is withdrawn from the study, the study staff will stop collecting new information about the subject. However, the study team will use the information they have already collected.

9) Risks to Subjects*

The risks associated with this study are largely those of the surgery itself. Additionally, the surgeon may not be comfortable using the new instrument, or the device may fail, which may lead to a delay during the exposure phase of the surgery. Also, as part of this research, there is a possibility of a breach of confidentiality (your private information) of your medical data. We will take adequate steps to protect your confidentiality. In addition, there may be uncommon or previously unknown risks that might occur.

10) Potential Benefits to Subjects*

Patients may benefit from a potential decrease in operative time, anesthesia time, and reduced blood loss.

11) Vulnerable Populations*

Not applicable.

12) Setting

The research will be conducted at Jackson Memorial Hospital.

13) Resources Available

All research personnel are CITI Certified.

Ludwig Medical Corporation will provide 40 devices free of charge for the study.

14) Recruitment Methods

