Surgeons in the Departments of Orthopedics and Neurological Surgery will refer eligible patients to the study. Subjects for the proposed study will be those who have already decided to undergo lumbar spine surgery. Subjects will be selected prospectively based on the proposed operative plan and randomized to one of the two groups (control vs suction-integrated Cobb groups).

15) Local Number of Subjects

Forty patients will be included.

16) Confidentiality

- Data will be stored on a password-protected computer in [name] office.
- Data will be coded and each subject will be assigned a unique study number. The linking code will be stored separately and will only be accessible to the study team.
- Only those research staff members approved by the IRB will have access to all research related data.

17) Provisions to Protect the Privacy Interests of Subjects

All data necessary and sufficient for the conduct of the study will be collected and stored as described in the "Confidentiality" section. This information will be both identifiable and non-identifiable data. General information will be collected about the patients from the medical records.

18) Compensation for Research-Related Injury

If injury should occur, treatment will be available. If subjects have insurance, their insurance company may or may not pay for these costs. If subjects do not have insurance, or if their insurance company refuses to pay, subjects will be expected to pay. Funds to compensate for pain, expenses, lost wages and other damages caused by injury are not available.

19) Economic Burden to Subjects

This study involves no financial cost to subjects.

20) Consent Process

Participants in this study will have already consented to surgery prior to being approached regarding participation in the study. Any concerns with the study or information collected will be discussed with the subjects.

Prior to surgery, the patient will be approached by the Investigator or one of the Sub-Investigators who will present a sample device and describe its function as well as the goal of the study. The patient will be given an opportunity to ask any questions about the device and the study. If the patient agrees to participate, he/she will be asked to sign the consent form.

Spanish-speaking participants will not be included in this study, as at this time there are no funds to translate the consent documents.

21) Process to Document Consent in Writing

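### The coin-toss closure rule closes only the device arm, so a fully randomised 20 + 20 results in about 6% of trials; the rest have predictable, non-randomised controls at the end or miss the stated arm sizes

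*Combined protocol and SAP*

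**What the plan says.** Section 5, Procedures Involved, sets out the allocation. "Randomization will be performed with a coin toss", the majority of three tosses deciding each patient's arm. "Randomization will stop once 20 subjects are enrolled in the suction-integrated Cobb group". Then: "If at that time, the control group has less than 20 subjects, all subsequent subjects will be assigned to the control group". There is no matching instruction for the control arm reaching 20 first. The same section also says "A total of 40 patients will be randomized, with twenty assigned to each group", and section 15 gives forty as the local number of subjects. The power paragraph, under section 6, assumes "a 1:1 enrollment ratio for sub-groups".

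Three other statements bear on the consequences. Recruitment Methods (section 14) says "Surgeons in the Departments of Orthopedics and Neurological Surgery will refer eligible patients to the study". Section 5 defines the main timing measure as "exposure time measured from skin incision until adequate exposure is achieved by the surgeon". It also says "Surgeons will be given time to become familiar with the instrument". Blinding and allocation concealment are not described, nor is who tosses the coin.

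**The concern.** The rule cannot reliably deliver what the same section promises. Any one trial can fail in only one of two ways.

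- **Device arm fills first.** The last patients are controls by rule, so it is not true that all 40 are randomised. Their allocation is known before they are approached.
- **Control arm passes 20 first.** Stopping at forty leaves fewer than 20 device cases. Tossing on until the device arm has 20 takes the total above forty.

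The first failure matters more. The surgeon necessarily knows which instrument is in use, surgeons choose whom to refer, and the end of exposure time is the surgeon's judgement. A foreseeable run of controls therefore leaves room for harder or easier cases to enter one arm only. Because these controls always come last, any drift in case mix or staffing also falls on one arm. Time to become familiar with the instrument partly covers learning with the device, but not that drift. No analysis of 40 patients can restore randomisation once it has been lost.

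**Working it through.** **Inputs.** From section 5: majority of three tosses, closure at 20 device patients, planned 20 + 20. From the power paragraph under section 6: control mean 30 min, ± 15, 45% reduction, alpha 0.05, power 80%, 36 subjects (18 per arm). Assumptions, because the documents do not state them: a fair coin, ± 15 is an SD common to both arms, and a two-sided test.

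**The plan's own sample size.** Difference = 0.45 × 30 = 13.5 min. The two-sided normal formula gives n per arm = 2 × (1.960 + 0.842)² × 15² / 13.5² = 19.4, so 20 per arm (40 in total), not 18. At 18 per arm, power is 77.0% (normal) or 74.6% (t test). This is a separate matter; the allocation results below do not depend on it.

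**Chance of each arm.** P(at least 2 heads in 3) = 3 × 0.5³ + 0.5³ = 0.5. Three tosses do the same as one.

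**Controls tossed before the 20th device patient.** Call this C. It is negative binomial: P(C = x) = C(19 + x, x) × 0.5^(20 + x).

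| Outcome | Probability |
|---|---|
| C < 20: device fills first, forced controls follow | 0.500 |
| C = 20: C(39, 20) × 0.5⁴⁰, all 40 tossed and split 20 + 20 | 0.063 |
| C > 20: control passes 20 first | 0.437 |

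A simulation of the three-toss rule (100,000 trials) gave 0.501, 0.062 and 0.437. Arm sizes of 20 + 20, however reached, occur in 50.0% + 6.3% = 56.3% of trials.

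**Size of the forced run, 20 − C.** Mean 5.0 when it occurs and 0.500 × 5.015 = 2.5 over all trials. It is 5 or more in 25.0% of trials and 8 or more in 10.8%.

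**Control passes 20 first.**
- Stopping at forty, device patients follow Binomial(40, 0.5): 17 or fewer in 21.5% of trials, 15 or fewer in 7.7%.
- Tossing on to 20 device patients adds 5.7 controls above 20, on average, when this happens.

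**An unwritten cap on both arms.** This would restore 20 + 20, but every trial would end with a forced run: mean 5.0, and 5 or more in 50.0%.

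**Power** (noncentral t, difference 13.5, SD 15): 79.2% at 20/20, 78.3% at 23/17, 76.6% at 25/15.

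**Illustration of bias.** The shift is assumed; the documents give none. If m of 20 controls are harder by s minutes, the comparison is biased by m × s / 20. For m = 5 and s = 5, 10 or 15, that is 1.25, 2.5 or 3.75 min. False-positive rates of a nominal 5% pooled t test (400,000 simulated trials per cell, 20 per arm, SD 15):

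| Forced controls | 5 min | 10 min | 15 min |
|---|---|---|---|
| 5 | 5.7% | 7.5% | 10.3% |
| 8 | 6.7% | 11.9% | 20.0% |
| Averaged over all trials, including those with no run | 5.4% | 6.8% | 9.1% |

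**The case against.** The strongest reply is that 6% makes the rule sound worse than it is. It counts one forced control (6.4% of trials) or a 21/19 split as failure. Half of trials have no forced run and 75% have fewer than five forced controls. This is fair as a caution: 6.3% is the chance of a fully randomised 20 + 20, and the 56.3% belongs beside it. But 50.0 of those 56.3 points include controls who were never randomised.

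Second, read literally, tossing continues until the device arm has 20, so the second failure means extra controls and not a short device arm. Power then rises, to about 84% at 26/20. That is correct, and it makes this branch mainly a conflict with the stated total of forty.

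Third, the bias is hypothetical. No passage says surgeons see the running count. Patients have already agreed to surgery, several eligibility criteria are objective, and the investigator or a sub-investigator, not simply the referring surgeon, approaches them (sections 14 and 20). Consent must also precede study procedures (section 21). These points reduce the risk. They do not remove it, because referral remains discretionary and, once the device arm is full, the allocation is known before consent is sought. The 20.0% figure does need a run of 8 and a shift of one full SD in every forced control.

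Fourth, blocks are also partly predictable. If every block boundary were known, the example list proposed below would contain 4 × 1.33 + 4 × 1.50 = 11.3 determined patients, whereas every toss before closure is unpredictable. This stands as a reason to vary the block sizes and keep them from recruiting staff.

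**Conclusion.** The concern holds. As written, the rule contradicts its own section: 93.7% of trials (50.0% + 43.7%) either end with non-randomised controls or miss the stated 20 + 20. This rests only on the text and a fair coin; a coin with a 45/55 bias lowers the fully randomised 20 + 20 from 6.3% to 4.0%. The main harm is a foreseeable, single-arm tail in an unblinded trial with discretionary referral and an endpoint closed by the surgeon's judgement. Loss of power from unequal arms is minor. The false-positive figures rest on an assumed shift and show what could happen; the documents do not show that it would. The case for changing the rule does not depend on them. The change must come before enrolment, because the allocation cannot be repaired afterwards.

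**What to change.** Replace the coin toss and closure rule in section 5 with one computer-generated, unstratified 1:1 list of exactly 40 assignments, 20 per arm, in permuted blocks of varying size. Four blocks of 4 and four of 6 in random order would do: 4 × 4 + 4 × 6 = 40. Delete the sentence that sends all later patients to control.

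Have someone outside recruitment prepare and hold the list. Conceal it in sequentially numbered, opaque, sealed envelopes or a database, and do not tell recruiting staff the block sizes. Open each assignment only after consent and eligibility are confirmed. Opening on the day of surgery is workable, since section 22 has the device brought in that day for each enrolled case. Stratify by department only if department totals are fixed in advance or a small departure from 20/20 is accepted.

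The cost is about an hour of a statistician's time, a set of envelopes and a short amendment, with no extra patients. The remaining weakness is that the end of a block can sometimes be guessed. At the end of the example list, the determined tail averages 1.33 patients after a block of 4 and 1.50 after a block of 6, or 1.4 overall. Its maximum is 3, and it falls in either arm. Under the present rule the forced run averages 5.0 when it occurs (2.5 over all trials) and always falls in the control arm.

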IRB Study Number: 20161061

Intraoperative Efficacy of Suction Enabled Retraction Device in Lumbar Spine Surgery

National Clinical Trial Number: **NCT03160170**

Study Number: 20161061

Date: March 15, 2017

Principal Investigator: [name]

1) Protocol Title

Intraoperative Efficacy of Suction Enabled Retraction Device in Lumbar Spine Surgery

2) Objectives*

This is a prospective randomized controlled trial of a new surgical instrument to assess:

- Effects on operative time and efficiency of exposure in open lumbar spine cases.
- Effect on total blood loss during the exposure part of the operation.
- Rate of clogging of suction device.

3) Background*

During spinal surgery, exposure of bony anatomy requires the use of retraction, suction, and electrocautery at the same time. As three instruments are generally used – a Cobb elevator, electrocautery, and suction – an assistant is generally required or the primary surgeon has to switch between the instruments. The resultant juggling of instruments and/or reliance on an assistant can influence operating time and efficiency.

The new device, Suction-Integrated Surgical Tissue Elevator & Retractor [SISTER], is shaped like a Cobb elevator but also has a hollow core allowing suction tubing to be connected. Thus, a single hand can be used to retract and suction at the same time while the other hand separates soft tissue from the bones with electrocautery. This set up which is proposed to be more efficient will be evaluated in this study.

The device is made of high density plastic material and is disposable. The device meets FDA's Medical Device Exemption 510(k) Requirements (Please see uploaded letter from Ludwig Medical Corporation).

4) Inclusion and Exclusion Criteria*

Inclusion

English-speaking patients undergoing Lumbar One to Sacral One open instrumentation performed by attending physicians in the Departments of Neurological Surgery and Orthopedic surgery will be included.

Exclusion

- Age less than 22 years old
- Patients whose procedure will not involve instrumentation

- Patients with prior Lumbar spine surgery involving more than one level
- BMI less than 20 or greater than 35
- Patients with known bleeding conditions (ex: Factor V Leiden, Von Willebrand's,)
- Patients that routinely take anticoagulation medicine (ex. Aspirin 325mg/day, Plavix)
- Operative cases where a single surgeon performs both sides of exposure.
- Pregnant women
- Prisoners
- Adults unable to consent

5) Procedures Involved*

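### No analysis of exposure time is specified, and adjusting for the planned number of levels would probably be more precise than the implied unadjusted comparison

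*Combined protocol and SAP*

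**What the plan says.** The sample-size paragraph in section 6 rests on exposure time: "an average exposure time with typical instruments of 30 (± 15) minutes, a 45% reduction in exposure time", with alpha 0.05 and 80% power. Section 7 then states "The data collected and planned analyses are described above". No earlier section names a test, model, effect measure, scale or covariate for exposure time or any other outcome.

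Three other passages bear on the choice of analysis:

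- Section 4 admits "English-speaking patients undergoing Lumbar One to Sacral One open instrumentation" and sets no limit on the number of levels to be operated.
- Section 5 says "The following data will be recorded: age, gender, BMI, spinal levels involved, overall operative time". It does not say whether the levels are those planned or those operated, or what they are for. It measures exposure time from skin incision to the point the surgeon considers adequate.
- Section 14 says "Subjects will be selected prospectively based on the proposed operative plan and randomized to one of the two groups". The planned extent of surgery is therefore known before allocation. Section 5 allocates by coin toss, without stratification.

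**The concern.** There are two linked problems.

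First, with no analysis fixed, the model, the scale (minutes or log minutes) and the covariates could all be chosen after the data are seen. In a 40-patient trial with several recorded patient variables, that leaves considerable freedom.

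Second, the only analysis the document implies is the unadjusted comparison of means behind the power calculation. Taking the allocation as given, that comparison is valid, and its standard error already allows for chance imbalance in extent. The issue is precision, not bias. Exposing a longer segment should take longer, so part of the 15-minute SD probably reflects case extent. An unadjusted analysis leaves that part in the error term. A usable baseline covariate is available at no cost but has been given no role.

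**Working it through.** **Inputs.** From section 6: control mean 30 min, SD 15 min (reading the ± as an SD), 45% reduction, alpha 0.05, power 80%, 1:1 allocation. From section 5: 20 per arm. The effect is 0.45 × 30 = 13.5 min, a standardised difference of 13.5/15 = 0.90. Assumed: two-sided testing, a common SD in the main calculation, exactly 20 per arm, and the share of variance R² that planned levels explain within arm. The documents do not give R².

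**The plan's own figure.** n per arm = 2 × [15 × (1.960 + 0.842)/13.5]² = 19.4. This rounds up to 20 per arm (40 in total), or 21 per arm with the t distribution. The stated 36 is not reproduced: 18 per arm gives 74.6% power by t-test (77.0% by normal approximation). That is a separate matter, and nothing below depends on it.

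**Unadjusted comparison, 20 per arm.** SE = 15 × √(2/20) = 4.74 min. With 38 df, t = 2.024, so the 95% CI half-width is 9.60 min. The noncentrality is 13.5/4.74 = 2.85, giving power 79.2%.

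**Adjusted for planned levels.** SE² = 15² × (2/20) × (1 − R²) × (1 + 1/(N − 4)), with N = 40 and 37 df (t = 2.026). The last factor, 37/36 = 1.028, is the average cost of chance imbalance in the covariate.

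| R² | SE (min) | Half-width (min) | Power |
|---|---|---|---|
| Unadjusted | 4.74 | 9.60 | 79.2% |
| 0 | 4.81 | 9.74 | 78.0% |
| 0.1 | 4.56 | 9.24 | 82.2% |
| 0.2 | 4.30 | 8.71 | 86.4% |
| 0.3 | 4.02 | 8.15 | 90.4% |

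Simulation at a common SD, with levels uniform on 1 to 5 (assumed), gives adjusted power of 78.1%, 82.6%, 86.5% and 90.5%.

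**Break-even.** The variances are equal when (1 − R²) × 37/36 = 1, that is R² = 1/37 = 0.027. Allowing for the lost degree of freedom, power is equal at about 0.028, a correlation of about 0.17.

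**Equivalent sample size.** The smallest unadjusted design reaching the adjusted power at R² = 0.1, 0.2 or 0.3 has 22, 25 or 28 per arm (83.0%, 87.7%, 91.1%). The middle figure is a strict threshold: 24 per arm gives 86.26% against 86.35%.

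**Unequal SDs.** A common SD of 15 around a device mean of 30 − 13.5 = 16.5 min would put Φ(−16.5/15) = 13.6% of normally distributed times below zero, so it is doubtful. If instead the SD falls in proportion to the mean (15 and 0.55 × 15 = 8.25, assumed), the SE is √[(15² + 8.25²)/20] = 3.83 min, unadjusted power is about 93% and the half-width is about 7.8 min. Simulated results for the adjusted model at R² = 0, 0.1, 0.2 and 0.3 are:

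- power 92.3%, 94.4%, 96.3% and 97.9%;
- half-width 7.80, 7.43, 7.04 and 6.63 min;
- type I error 5.0% to 5.1% with equal arms.

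**The case against.** The strongest counter-argument is that the certain defect is the missing analysis, while the covariate is an optional efficiency choice whose benefit cannot be established from the documents. No passage links levels to exposure time or gives the mix of levels. If most patients have a similar number of levels, R² could be small and adjustment would gain nothing. The larger power gains also need the common SD that the check itself finds doubtful. With SDs of 15 and 8.25, the change in power is only about −1 to +5 points.

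Much of this is right. The size of the gain is unknown, and the power argument weakens under unequal SDs. What remains is the asymmetry: break-even is near 3% of variance, the worst expected loss is about one point of power, and the interval narrows under either SD assumption once R² reaches 0.1.

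It can also be said that section 8 is weak evidence that planned and operated levels differ, because it concerns changes that make a patient ineligible. That is fair. The case for recording planned levels rests instead on section 5 not saying which is meant. Levels recorded at or after surgery may not be a pre-randomisation value.

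**Conclusion.** The concern holds and the plan should be changed. That no analysis is stated is plain from the text. That adjustment for planned levels would be more precise is probable, not certain. With a common SD of 15 and 20 per arm, power moves from 79.2% to between 82.2% and 90.4% for R² of 0.1 to 0.3, and falls to 78.0% if levels explain nothing. If the SD falls with the mean, the benefit shows mainly in the interval: the half-width goes from about 7.8 min to 7.4, 7.0 or 6.6 min at R² of 0.1, 0.2 or 0.3. The R² values, two-sided testing and exact 20:20 split are assumptions. Adjustment does not address any weakness in the coin-toss allocation itself.

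**What to change.** - Record the planned number of levels on the case form before the coin toss, separately from the levels operated.
- State the primary analysis: a linear model of exposure time on arm, adjusted for planned number of levels, reporting the adjusted difference in minutes with its 95% CI.
- Fix in advance how skew and unequal variance will be handled. A named log-scale sensitivity analysis is one option, and fits the relative form of the assumed effect. HC3 robust standard errors are another; if made primary they cost about two further points of power in simulation and move break-even R² to about 0.09.
- Keep to the one covariate unless there is reason to expect more. BMI (already restricted by the exclusion "BMI less than 20 or greater than 35") and department would together need to add about 4 to 6 percentage points of R² beyond levels to repay their cost at N = 40.
- Consider the same covariate for blood loss during exposure. No figures are available to size that gain.

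The cost is a few lines of text and one form entry, with no extra patients or visits. Statistically it is one degree of freedom, and about one point of power if levels turn out to be unrelated to exposure time.

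### Exposure time, the only outcome in the power calculation, stops at an undefined judgement of adequacy in an unblinded operation; fix one observable end point before the first case

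*Combined protocol and SAP*

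**What the plan says.** Section 2 lists three objectives. The first is "Effects on operative time and efficiency of exposure in open lumbar spine cases" and the second is "Effect on total blood loss during the exposure part of the operation"; the third concerns clogging of the suction. None is labelled primary.

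Section 5 lists the data to be recorded. They include overall operative time, "exposure time measured from skin incision until adequate exposure is achieved by the surgeon", and "blood loss during the exposure, and number of times the suction had to be unclogged". No section says what makes an exposure adequate, which sides or levels it must cover, or who notes the time.

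Section 5 also says: "In the suction-integrated Cobb group, surgeons will be provided with the device". The surgeon therefore cannot be blinded.

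The power paragraph, printed under section 6, uses exposure time only. Its inputs are "an average exposure time with typical instruments of 30 (± 15) minutes" and "a 45% reduction in exposure time previously demonstrated in a previous small study with the new device". Operative time, blood loss and clogging have no power assumptions.

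Two exclusions in section 4 bear on the remedy. One is "Patients whose procedure will not involve instrumentation", so every completed eligible case has an instrumentation step. The other removes cases in which one surgeon exposes both sides, so more than one surgeon takes part in each exposure.

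**The concern.** Unblinding is unavoidable in a trial of a hand-held instrument, but an undefined stop point is not. Together they leave the trial open to differential measurement. If one arm tends to be judged adequately exposed at an earlier stage of dissection than the other, that difference goes straight into the estimated effect. Randomisation does not remove it and a larger sample would not dilute it.

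The effect can go either way. Early calling in the device arm would look like time saved; late calling would hide a real saving. Blood loss during exposure is counted over the same interval, so a second objective shares the weakness. Because each exposure involves more than one surgeon, it is also unclear whose judgement, or which side, ends the interval.

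**Working it through.** **Inputs.** From the power paragraph: control mean 30 min; ±15 min, which the document does not label and gives for typical instruments only (here read as an SD and assumed equal in both arms); 45% reduction; alpha 0.05 (two-sided assumed); power 80%. From section 5: 20 per arm. The shifts of 2, 3 and 5 min are assumptions.

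**The plan's own figure.** Planned effect = 0.45 × 30 = 13.5 min; standardised effect = 13.5/15 = 0.90. The plan states 18 per arm (36 in total). A two-sided calculation gives 20 per arm by the normal approximation and 21 by the t test (20.4 rounded up), so 36 does not reproduce. That is a separate matter: at the planned 20 per arm, t-test power is 79.2%, close to target, and nothing below depends on 36.

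**Significance threshold.** SE = 15 × √(2/20) = 4.74 min. With 38 degrees of freedom the critical t is 2.024, so an observed difference of 2.024 × 4.74 = 9.60 min is needed.

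**No true effect, stop point shifted by b minutes in one arm.** The test statistic is noncentral t with 38 df and noncentrality b/4.74.

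| Assumed shift b | Noncentrality | False-positive rate |
|---|---|---|
| 0 | 0 | 5.0% |
| 2 min | 0.42 | 7.0% |
| 3 min | 0.63 | 9.5% |
| 5 min | 1.05 | 17.7% |

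At 5 min, 17.6 of the 17.7 percentage points lie in the direction of the shift.

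**True effect of 13.5 min, end called b minutes later in the device arm.** The apparent effect is 13.5 − b.

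| Assumed shift b | Apparent effect | Power |
|---|---|---|
| 0 | 13.5 min | 79% |
| 2 min | 11.5 min | 66% |
| 3 min | 10.5 min | 58% |
| 5 min | 8.5 min | 42% |

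**What a first-instrumentation time stamp could add.** Suppose the work between exposure and first instrumentation adds an independent SD of s minutes (assumed). The SD of incision-to-first-instrumentation time is √(15² + s²), and the 95% CI half-width is 2.024 × SD × √(2/20).

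| Assumed s | SD | 95% CI half-width | Power for 13.5 min |
|---|---|---|---|
| 5 min | 15.8 min | 10.1 min | 75% |
| 10 min | 18.0 min | 11.5 min | 64% |
| 15 min | 21.2 min | 13.6 min | 50% |

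For exposure time the half-width is 9.6 min. A simulation with no true effect and a 5 min early call in the device arm looked only at trials whose exposure-time result falsely favoured the device. In those trials the first-instrumentation estimate still pointed towards the device in about 99.8%, 97% and 90% (s = 5, 10, 15), and it was significant in 12% to 14%. A non-significant supporting result is thus usual under biased calling, but it also occurs in 25%, 36% or 50% of trials with a real 13.5 min benefit.

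**The case against.** The strongest reply is that the harm is hypothetical. No passage shows that calling differs between arms, and every harmful figure rests on an assumed uniform shift. This stands. Shifts of 3 min or less do modest harm, and the larger figures need about 5 min, a sixth of the 30 min control mean. The point is therefore about vulnerability.

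The wording is also open: an exposure achieved by the surgeon may mean only that the surgeon does the dissecting, not that the surgeon declares the end. That is a fair reading, but no alternative judge, criterion or recorder is named, so the gap remains.

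Overall operative time is recorded, belongs to the first objective and does not depend on this judgement. It is a real but partial safeguard: it covers the whole operation, and the documents give no SD or power for it.

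A reader might infer two stronger things. The first is that the trial is biased in favour of the device; the documents support neither a direction nor a size, and late calling would act against the device. The second is that a first-instrumentation time stamp would detect or cure the problem. It would seldom separate biased calling from imprecision in a single trial of 40. Simulating that comparison with first-instrumentation time assumed unaffected does return a 5% error rate, but that follows from the assumption and is no evidence that the remedy works. The first instrumentation step is itself partly paced by the unblinded surgeon.

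**Conclusion.** The concern holds as a correctable weakness in the outcome definition. This is more than a missing detail, because following the stated rule exactly still allows the stop point to differ by arm, in the only outcome in the power calculation and in exposure blood loss.

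Its actual size is unknown. The illustrations rest on 20 per arm, ±15 being an SD common to both arms, a two-sided t test and a uniform assumed shift. Confidence is firm on what the documents say and medium on how much it matters in practice. The change should be made, and the value lies mainly in the definition; the extra time stamp is secondary.

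**What to change.** **Main change, in section 5.** Before the first case, the investigators set one observable criterion for the end of exposure. It should be the same in both arms, cover both sides and all planned levels, and be used for exposure time and exposure blood loss alike. Someone already present, other than the operating surgeons, records the clock time. The documents do not describe room staff, so the availability of such a person is assumed.

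**Secondary change.** Also record the clock time of a pre-defined first instrumentation step. Report the arm difference in incision-to-first-instrumentation time with a 95% CI, as descriptive support only, with no rule that lets it confirm or overturn the exposure-time result.

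**Cost.** One written criterion, one extra time stamp per case and a small added analysis, with no change in sample size. The recorder can still see which instrument is in use, so the bias is reduced, not removed. The criterion has to be in place from the start, since an end point not noted during surgery may be impossible to recover afterwards.
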